5.2. Reference Dates

- Age and time from diagnosis uses the enrollment date as its reference date.
- Safety data, such as AEs and laboratory assessments will use the first treatment date as a reference date.
- Efficacy data will use the first date of study treatment as a reference date.
- Study day will be based on the date of first study treatment as a reference date.

The date of first study treatment will be based on the first date on which any therapy component was taken.

Sponsor: Aduro Biotech, Inc.
Protocol Number: ADU-CL-11
Version and Date: Version 1.0, 03MAY2018

5.3. Study Day and Duration Variables

Reference date calculations will be defined as the following:

- date of interest – reference date + 1 when the date of interest \geq reference date;
- otherwise, date of interest – reference date.

For instance, study day will be based on the date of first study treatment as the reference would either have a negative value if collected before dosing or a positive value if collected after drug dosing; there will be no study day zero.

Duration of time is dependent on reference dates and will be calculated in a manner similar to that of the reference date calculation, assuming that dates of interest will strictly follow reference dates (e.g. no negative values). For example, duration on study treatment is defined as the end of study date – first dose date + 1. Duration of treatment is defined as the last date of treatment – first dose date + 1. Duration of the safety observation period is defined as (the last date of treatment + 30 days) – first dose date + 1. Subjects still receiving ongoing treatment or participating in study follow up at the time of analysis will use imputed treatment end and end of study dates as described in Section 5.6.

Survival, or time-to-event, endpoints such as progression-free survival (PFS) or overall survival (OS) are followed until first event or censoring. As a result, survival time will be calculated as: event or censoring date – reference date + 1. These are further described in Section 7.

When reporting survival or duration outcomes, the results (in days) above will be converted to an appropriate unit. When reporting in months it will be divided by 30.4375; for reporting in weeks it will be divided by 7; and for reporting in years it will be divided by 365.25.

5.4. Study Time Periods

Safety reporting will be classified by the following study periods for analysis:

Pre-therapy is defined as the period prior to a subject's first dose of study treatment.

On therapy is defined as the period between first dose of study treatment and within 30 days following the last dose of study treatment.

Post-therapy is defined as the period of time following the on therapy period.

5.5. Baseline, Post-Baseline Changes, and Endpoint

Sponsor: Aduro Biotech, Inc.
Protocol Number: ADU-CL-11
Version and Date: Version 1.0, 03MAY2018

Baseline will be based on the last nonmissing value collected prior to or on the date [and time, if applicable] of first study treatment. Post-baseline values will be those collected after first dose of study drug.

Change from baseline is defined as: value – baseline value.

Percentage change from baseline is defined as: (value – baseline value)/baseline value X 100%.

Most extreme change: The maximum most extreme change will be the maximum post-baseline value; the minimum most extreme change will be the smallest post-baseline value. This calculation will consider all assessments collected within the on therapy period, scheduled or unscheduled.

5.6. Imputation of Partial Dates

Adverse Events and Concomitant Medications

- If the AE start date is completely missing, no imputation will be conducted.
- If the AE start date is missing day and month, do the following:
 - If the treatment start date is missing or the AE year does not fall in the same as that of first treatment or if the AE contains information to indicate that the event ended before the date of first study treatment (e.g. AE end date month and year are earlier than the treatment start date or the full date is known and occurs earlier than the date of first treatment), then set the start month and day to January 1st
 - Otherwise, set the start date to the date of first study treatment
- If only the day is missing, do the following:
 - If the study treatment start date is missing or the month and year does not fall in the same as that of first treatment or if the AE contains information to indicate that the event ended before the date of first study treatment, then set the start month and day to the 1st of the stated month
 - Otherwise, set the start date to the date of first study treatment
- End dates will not be imputed

Subsequent Anticancer Therapy, Radiotherapy or Anticancer Surgical Procedures

Partial dates for subsequent therapies will not typically be imputed, but may be needed to support efficacy outcome derivations (e.g. PFS censoring dates). In this case, the following will be applied for imputation of new anti-cancer therapies taken after first study treatment:

- If the start date is completely missing, no imputation will be conducted
- If the start date is missing day and month, do the following:
 - If progressive disease (PD) has been identified in the year noted, new anti-cancer therapy date will be assigned to begin one day after the date of PD.
 - Otherwise the new anti-cancer therapy date will be assigned to January 1st.
- If only the day is missing, do the following:

Sponsor: Aduro Biotech, Inc.
Protocol Number: ADU-CL-11
Version and Date: Version 1.0, 03MAY2018

- If PD has been identified in the year noted, new anti-cancer therapy date will be assigned to begin one day after the date of PD.
- Otherwise the new anti-cancer therapy date will be assigned to the 1st of the stated month.

Overall Response Date

For each visit-specific disease assessment, the date of overall response will need to be established. For complete response (CR) and partial response (PR), set the date of overall response to the latest of all tumor assessments for the specified visit. Otherwise, set to the earliest date of all assessments made during the specified visit.

Treatment End Date

Missing treatment end dates will not necessarily be imputed at the end of the study. However, due to ongoing reporting needs, treatment end date will be imputed as the earliest of the data cutoff date, date of death, or date of treatment study withdrawal.

End of Study Date

Missing study end dates will not necessarily be imputed at the end of the study. However, due to ongoing reporting needs, end of study dates will be imputed as the earliest of the data cutoff date or date of death.

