7.1. Efficacy Endpoints and Analyses

Refer to Section 2 for further details on Phase 1 and Phase 2 efficacy endpoint hierarchy.

Objective Response Rate

For purposes of mRECIST based derivations, a subject's best overall response (BOR) is determined by the highest qualitative value assessed during the study given a hierarchy of overall response results: CR > PR > SD > PD > NE. In order for a valid value of SD to be assigned, there must be evidence of stable disease for at least 8 weeks. If the minimum time for SD has not been met on the first assessment, the assignment of BOR will depend on subsequent response assessments. Subjects which do not have follow up data after a first assessment of SD prior to the minimum time requirement will be considered as not evaluable. BOR will be based on assessments collected after the first dose of study until confirmed disease progression; assessments collected after the start of new cancer treatment will not be considered.

The objective response rate (ORR) is defined as the number of subjects who exhibit a BOR response of CR or PR divided by the number of evaluable subjects. Subjects who discontinue prior to any evaluation of post-baseline tumor assessments will be considered as non-responders regardless of discontinuation reason. ORR will not be reported in the CSR synopsis.

BOR will be listed for each subject.

Progression-Free Survival

PFS is defined as the number of weeks from the date of first dose of study treatment to the first date of objectively determined progressive disease or death from any cause and is computed as described in Section 5.3. The primary analysis of PFS will include tumor assessments collected after the end of study treatment and will be based on mRECIST criteria for progressive disease confirmation. Tumor assessments taken after switch to another anti-cancer therapy will be excluded from consideration.

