The first date of objectively determined progressive disease would be the earliest date of any post-baseline overall response finding of progressive disease is confirmed as part of the tumor lesion assessment data or death, unless a subject is censored at an earlier date. If an assessment occurs over several days, the method described in Section 5.6 will be used. If there are no adequate assessments for a subject, they will be censored on their first dose date unless they died prior to having their first assessment (in which case they will be considered to have had a PFS event of death). If a subject receives subsequent anticancer therapy prior to documentation of

Sponsor: Aduro Biotech, Inc.
Protocol Number: ADU-CL-11
Version and Date: Version 1.0, 03MAY2018

progressive disease, PFS will be censored at the latest adequate assessment prior to therapy initiation.

Subjects who progress or die following an extended period of follow up will also be censored at a latest adequate assessment prior to the end of a predefined lapse window, even if information is available regarding progression or death after this extended period. Should a subject die after the end of this lapse window they will be censored at their first dose date. The lapse window after which PFS events will not be considered is defined in Section 5.7.

If a subject does not receive confirmation of radiologically identified PD, and there are no further assessments prior to censoring, the subject will be considered to have progressed based on their last valid assessment.

Otherwise, if a subject does not have documented progression, the subject will be censored at the latest adequate assessment.

PFS will be listed for each subject.

Disease Control Rate

Disease control rate (DCR) is defined as the number of subjects who exhibit a BOR response of CR, PR or SD divided by the number of evaluable subjects.

The derivation analysis of DCR will be produced based on mRECIST, RECIST 1.1, and GCIG CA-125 criteria. A description of BOR derivations for RECIST 1.1 and GCIG CA-125 can be found in a previous section.

DCR will not be reported in the CSR synopsis. BOR will be listed for each subject.

Duration of Response

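### SAP 5.6 dates a new anticancer therapy without using a known month and without a lower bound, which can misstate individual PFS and best overall response

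*SAP*

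**What the plan says.** SAP section 5.6 limits the imputation to efficacy needs: "Partial dates for subsequent therapies will not typically be imputed, but may be needed to support efficacy outcome derivations (e.g. PFS censoring dates". It covers therapy, radiotherapy and anticancer surgery, and states that "the following will be applied for imputation of new anti-cancer therapies taken after first study treatment". There are two branches.

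- **Day and month missing.** If PD was identified in the stated year, the therapy starts the day after PD. If not: "Otherwise the new anti-cancer therapy date will be assigned to January 1st".
- **Only the day missing.** "If PD has been identified in the year noted, new anti-cancer therapy date will be assigned to begin one day after the date of PD". If not: "Otherwise the new anti-cancer therapy date will be assigned to the 1st of the stated month".

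The adverse-event rule in the same section compares the partial date with first study treatment. If the event may fall on treatment, the instruction is: "Otherwise, set the start date to the date of first study treatment".

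The therapy date then drives SAP section 7.1. For PFS, "Tumor assessments taken after switch to another anti-cancer therapy will be excluded from consideration", and if therapy precedes documented PD, "PFS will be censored at the latest adequate assessment prior to therapy initiation". A subject with no adequate assessment is censored at first dose, unless she died before the first assessment. Best overall response (BOR) ignores scans after the start of new cancer treatment. Duration of response (DOR) uses censoring similar to that for PFS.

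**The concern.** The day-missing branch repeats the year test of the branch above it, although the month is now known. A therapy recorded as starting before PD can therefore be moved to the day after PD. Progression on another drug then counts as progression on study treatment, which is what the section 7.1 censoring rule is meant to prevent.

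The 1 January rule applies only to therapies taken after first study treatment, yet it can give a date before that treatment. Every on-study scan then comes after the supposed switch and is discarded.

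At stake are the individual PFS time and status, BOR and DOR.

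**Working it through.** The plan gives no figure to reproduce, so the check follows the rules literally through assumed subjects. The documents contain no subject-level dates.

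**Inputs**
- Study day = date − first dose date + 1 (SAP 5.3).
- PFS and BOR rules as above (SAP 7.1).
- Imaging every 9 weeks = 63 days (Protocol 8.1.2).
- Lapse window after which a PFS event no longer counts: 18 × 7 + 14 = 140 days (SAP 5.7).
- All subject dates below are assumptions.

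**Case 1: month known and before PD.** First dose 1 February 2017. Scan without PD on 5 April: 63 days later, day 64. Therapy recorded as May 2017. PD on a recorded standard-of-care scan on 7 June: 126 days after first dose, day 127.
- Any day in May lies between the two scans, so the right answer does not depend on the missing day: censored at day 64.
- The rule finds PD in 2017 and imputes 8 June 2017. PD now precedes therapy, so PFS is an event at day 127.
- The gap from 5 April to 7 June is 63 days, inside the 140-day window, so the lapse rule does not remove the event.
- BOR changes in this branch only if a scan between the real start and the imputed date is better than the earlier ones.

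**Case 2: month known and after PD.** First dose 10 January 2017, PD on 14 March (day 64), therapy recorded as December 2017.
- The rule imputes 15 March 2017.
- The PFS event stays at day 64.
- Scans after 15 March drop out of BOR. BOR already stops at confirmed progression, so it can change only if that PD was not confirmed.

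**Case 3: year only, no PD in that year.** The rule imputes 1 January 2017.
- First dose 15 June 2017: 15 June − 1 January = 165 days before first dose.
- First dose 15 May 2017: 134 days before. With scans on 17 July, 18 September and 20 November (days 64, 127, 190) and a true start of 10 December, PFS should be censored at day 190 with three scans usable for BOR. Under the rule no scan counts, PFS is censored at day 1 and BOR is not evaluable.
- The same happens if PD is found only in the next year, for example on 22 January 2018 with a true start of 20 December 2017.

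**Case 4: only the day missing, no PD in that year.** The 1st of the month precedes first dose only if therapy began in the same month as first dose. With first dose on 15 May, therapy on 29 May and a first scan in July, PFS is censored at day 1 under either date, so nothing changes.

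| Case | Imputed start | PFS under the rule | PFS with true start |
|---|---|---|---|
| 1 | 8 June 2017 | event, day 127 | censored, day 64 |
| 2 | 15 March 2017 | event, day 64 | event, day 64 |
| 3 (first dose 15 May) | 1 January 2017 | censored, day 1 | censored, day 190 |
| 4 | 1 May 2017 | censored, day 1 | censored, day 1 |

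**The case against.** **The lapse rule removes most large shifts.** A reader might infer that a therapy recorded many months before PD would lengthen PFS by that whole interval. The documents do not generally support this. Scheduled imaging stops at new anticancer therapy (Protocol 6.5 and 8.1.2), and SAP 5.7 and 7.1 disregard progression after a 140-day lapse. Take the Case 1 subject with PD on 11 October 2017 (day 253) instead. If no scan was recorded after day 64, the gap is 253 − 64 = 189 days, and PFS is censored at day 64 whichever therapy date is used. The event at day 253 appears only if interim scans were recorded after the switch. That is possible, since the Phase 2 schedule's tumor evaluation note allows standard-of-care scans to be collected, but it is a condition.

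**Treatment-emergent flags.** A reader might also infer that a pre-dose therapy date closes the treatment-emergent adverse-event window before treatment began. SAP 8.1 does end that window at subsequent therapy, but it does not refer to section 5.6, which reserves the imputation for efficacy. Those flags are affected only if a programmer reuses the imputed date. All adverse events are listed in any case.

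**The consequences are small.** SAP section 9 plans no efficacy summaries, section 7.1 leaves ORR and DCR out of the synopsis, and section 4 plans no tests. The subsequent-therapy record is listed too, so a reader can see the partial date. This stands, and it lowers the severity. It does not make the rule right: the listings are the only efficacy output.

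**The scope wording already limits the rule.** It selects therapies taken after first study treatment, but it does not bound the date assigned to them.

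**Conclusion.** Wrong as written, minor severity.

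1. The day-missing branch ignores the known month when PD fell in the same year. PFS can change from censored to event when the recorded month precedes PD and a post-therapy scan showing PD was recorded within the lapse window (day 64 censored against day 127 event in the assumed case). When the recorded month follows PD, the PFS event is unchanged, and BOR can change only if that PD was not confirmed.
2. The 1 January assignment has no lower bound. For a subject first dosed later in the stated year with no PD identified in that year, it falls before first dose and discards every on-study scan. The condition of no PD in that year is essential; with PD, the rule gives the day after PD.

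DOR can be affected through its similar censoring. The effect is confined to individual lines in the efficacy listings. The documents do not say how many therapy dates are partial, so the number of affected subjects could be zero.

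**What to change.** - **Only the day missing:** test for PD in the stated month and year. If found, use the day after PD; otherwise use the 1st of the stated month. In Case 1 this gives 1 May 2017 and restores censoring at day 64.
- **All branches:** keep the imputed date within the known month or year and never before first study dose.
- **Therapies recorded as started after study drug discontinuation** (the premise of SAP 6.7): set the date no earlier than the day after last study dose, still within the known period. A first-dose floor alone would leave Case 3 censored at day 1. With this floor, the 15 May subject is censored at day 190 if last dose was on or after 20 November, and at day 127 if it was from 18 September to 19 November.
- **Radiotherapy or other therapy recorded as given during treatment:** do not apply the last-dose floor, because it would post-date the therapy and retain scans taken after it.

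The cost is a few words in section 5.6 and a date bound in the derivation code. There is one small downside: a therapy that really began before last dose, but is not recorded as such, would be dated slightly late. It would also help to state in SAP 8.1 whether the imputed date may be used for the adverse-event window.

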5.7. Lost to Follow Up or Lapse of Adequate Assessments

If a subject has missed two or more scheduled disease assessments, a censoring date will be required in support of relevant survival endpoint derivations. For example, PFS will be censored at the last adequate disease assessment prior to the lost to follow up window. However, this survival outcome would be considered censored after an extended amount of time without additional assessment (after two have been missed). Based on a protocol specified disease assessment schedule of every 9 weeks, a window of 140 days [18 weeks + 14 days] would be used as the censoring date (assuming a protocol window period of 7 days for each assessment).

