10.2.1.2 Progression-Free Survival

PFS is defined as the time from the date of first dose to PD or death due to any cause. Subjects who do not experience PD and do not die on or before the data cut-off date will be censored at the time of last tumor assessment or data cut-off date, whichever is earlier. Subjects who do not experience PD and start new systemic therapy will be censored at the time the new systemic therapy was begun or the data cut-off date, whichever is earlier. Subjects with no assessments of PD will be censored at the time of first dose. Subjects who are lost to follow up for assessment of PD will be censored at their last tumor assessment or data cut-off date whichever is earlier. Kaplan-Meier methodology will be used to estimate median PFS for each cohort in Phase 1 and in each Arm in Phase 2.

The primary definition of PD for PFS is based on mRECIST. Analyses will be performed separately using objective disease responses definitions based on the mRECIST, RECIST v1.1, and GCIG CA-125 criteria. Analysis repeated for RECIST v1.1 and GCIG CA-125 are considered supportive.

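### SAP 5.7 gives two censoring points for a subject who lapses from scanning: the last adequate assessment, and a 140-day window with no start point

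*SAP*

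**What the plan says.** SAP 5.7 sets the trigger: "If a subject has missed two or more scheduled disease assessments, a censoring date will be required". It then gives the censoring point as an example: "PFS will be censored at the last adequate disease assessment prior to the lost to follow up window". After a sentence saying that the outcome counts as censored once two assessments have been missed, it closes with: "a window of 140 days [18 weeks + 14 days] would be used as the censoring date". It builds the 140 days from a "protocol specified disease assessment schedule of every 9 weeks", "assuming a protocol window period of 7 days for each assessment".

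Two other places cover the same subject:

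- SAP 7.1, under Progression-Free Survival, says that subjects who progress or die after an extended period "will also be censored at a latest adequate assessment prior to the end of a predefined lapse window". It refers to SAP 5.7 for the window beyond which PFS events no longer count. Its next rule differs: a subject who dies after the window is censored at the first dose date.
- Protocol 10.2.1.2 says "Subjects who are lost to follow up for assessment of PD will be censored at their last tumor assessment", or at the data cut-off if that is earlier.

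SAP 7.1 also applies similar censoring to DOR.

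**The concern.** A programmer needs one date per subject, because SAP 5.3 computes survival time as the event or censoring date minus the reference date plus one. For a lapsed subject, SAP 5.7 supplies a date (the last adequate assessment) and then a duration described as a date. The two cannot both be the censoring point.

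The difference has a direction. Censoring at the last adequate assessment credits only time over which progression was actually checked. Carrying the subject forward through the window keeps her event-free and at risk while nobody was looking. PFS by mRECIST is a Phase 2 primary endpoint, and SAP 7.1 sends the reader to SAP 5.7 for the window, so the sentence may well be used when the specification is written.

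**Working it through.** **Inputs.** Trigger of two missed assessments, 9-week interval and 7-day allowance: SAP 5.7. Conversion: "When reporting in months it will be divided by 30.4375" (SAP 5.3). SAP 7.1 defines PFS in weeks, so both units are shown.

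**1. The SAP's own figure.** Two intervals plus two allowances: 2 × (9 × 7) + 2 × 7 = 126 + 14 = 140 days. This reproduces the SAP. Built this way, 140 days is the longest gap from one scan to the second scan after it within the visit windows. That fits a lapse threshold counted from the last scan.

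**2. Its length.** 140 / 30.4375 = 4.60 months; 140 / 7 = 20.0 weeks.

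**3. One subject, last adequate scan on study day 63, no event recorded.** The SAP gives no start point, so the second row assumes that the 140 days run from that scan.

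| Reading | Censoring day | Months | Weeks |
|---|---|---|---|
| Last adequate assessment | 63 | 63 / 30.4375 = 2.07 | 9.0 |
| 140-day window taken as the date | 63 + 140 = 203 | 203 / 30.4375 = 6.67 | 29.0 |

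The unassessed time credited is 0 days in the first row and 140 in the second. It would be less than 140 if the data cut-off fell inside the window and were applied as a cap, hence up to 140 days.

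**4. Why the missing start point matters.** If the 140 days ran from first dose, every lapsed subject would be censored at about day 140. For someone last scanned at week 27 (27 × 7 = day 189), that is 189 − 140 = 49 days before a scan showing her progression-free. No sensible rule does this, but nothing in SAP 5.7 excludes it.

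**5. The passages side by side.** SAP 5.7 (example sentence), SAP 7.1 (main lapse rule) and Protocol 10.2.1.2 all point to the last assessment. SAP 5.7 (last sentence) points to the window. SAP 7.1 (death rule) points to the first dose date. A subject who lapses and later dies therefore has three candidate dates.

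**6. What it could do to a median, if someone computed one.** The documents give no lapse rates, so everything here beyond n = 27 and the null median of 3.6 months (Protocol 10.2.4) is assumed. Event times are exponential, no data cut-off is applied, and the quantity is the chance that the Kaplan-Meier median reaches 4.8 months.

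- Progression dated at the next 63-day scan, lapse after day 63 or 126, about 6%, 11% and 17% of subjects censored by lapse: 0.34, 0.39 and 0.43 under the 140-day date, against about 0.31 under last-assessment censoring. With no lapses it is 0.30, so most of the level comes from the scan grid. The differences are about 0.03, 0.08 and 0.12.
- Progression observed continuously, last scan at baseline, week 9 or week 18, with 10%, 20% and 30% assigned to be lost: 22% against 14%, 33% against 15%, and 46% against 16%. The differences are 8, 18 and 30 percentage points.

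The direction is the same in both. The size depends almost entirely on the assumptions.

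**The case against.** The strongest reply is that the right rule is already in place. SAP 7.1 is the PFS definition. It censors at the latest adequate assessment and takes from SAP 5.7 only a window, as the limit beyond which events do not count. The protocol agrees, and so does the earlier sentence in SAP 5.7. A competent programmer reading all of these would treat 140 days as a threshold. This stands as the most likely intent, and it rules out one tempting inference: that the sponsor decided to credit 4.6 months of unobserved time.

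The second reply concerns consequence. The SAP is an abbreviated plan for a CSR synopsis, written after the sponsor ended development. SAP 9 says that efficacy endpoints are derived and listed but not summarised; SAP 4 plans no significance tests; and the appendices contain no efficacy table and no figure. This also stands, and it rules out a second inference: that the plan biases median PFS upward against the 4.8-month bar. SAP 3.3 and 3.4 restate that bar, but no planned output compares a median with it. The tumour assessment and response listings would also let a careful reader spot a date that matches no scan.

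Neither reply removes the contradiction. The sentence remains in the section that SAP 7.1 cites, and the listings are the only PFS output planned.

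**Conclusion.** The contradiction in SAP 5.7 is real and should be corrected. It is a wording defect that could be mis-programmed, not a settled rule. Read with SAP 7.1 and Protocol 10.2.1.2, the 140 days is most likely the gap that defines a lapse.

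Taken literally, it would add up to 140 days (4.60 months, 20.0 weeks) of unassessed progression-free time for each lapsed subject. This assumes that the 140 days run from the last adequate assessment, which the SAP does not state. The direct effect is on per-subject dates in Listing 16.2.6.2.6 (PFS) and, if there are responders, Listing 16.2.6.2.7 (DOR).

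A median would be biased upward only if someone later computed one from those dates, by an amount that depends on lapse rates the documents do not give. The simulated figures illustrate direction only and should not be cited as an estimate for this trial.

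**What to change.** Replace the last sentence of SAP 5.7 with:

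*A gap of more than 140 days (18 weeks + 14 days) since the last adequate assessment defines the lapse window; PD or death after that gap is not counted as an event, and PFS and DOR are censored at the last adequate assessment before the gap.*

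Then reconcile the SAP 7.1 rule that censors a death after the window at the first dose date. As written, it conflicts with the sentence above and with the SAP 7.1 sentence just before it, which already covers subjects who die after an extended period. If it was meant only for subjects with no adequate post-baseline assessment, SAP 7.1 should say so; otherwise it should be removed. Either way, each lapsed subject should end with a single censoring date.

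Cost: one sentence in SAP 5.7, one clarification in SAP 7.1 and one line of programming specification. No new data are needed. If the listings have already been produced, check the censoring date of each subject with two or more missed assessments against her last adequate scan.
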